5.8.4 Study Justification in Relation to Risk

The sponsor believes that any additional risks presented by participating in this study are very low and that adequate testing, safeguards, and risk monitoring have been incorporated into the study to further minimize and mitigate the risks relative to the potential benefits, including relief from symptoms of nasal obstruction, that may be realized by participation in this study.

5.8.5 Benefits

The potential benefit associated with the Vivaer procedure is to offer a minimally invasive treatment method that has been shown in a previous study to help alleviate symptoms of nasal obstruction and which has been cleared for use by the FDA and is CE-marked in the European Union. The Vivaer ARC Stylus improves nasal breathing by modifying the tissues of the nasal airway using low doses of RF energy. The low-power RF energy generates heat within the tissue and creates a coagulation lesion. As the lesion heals, the tissue retracts and stiffens, thereby decreasing NAO and improving airflow. In addition to symptom relief after correcting nasal obstruction, participants may also experience better sleep function and better psychological function. (eg, concentration, productivity, and frustration). These benefits may last beyond the length of the study.

6.0 Study Schedule and Procedures

This section provides summaries of the study Schedule of Events and flow of participants through the study, as well as more detailed information on study procedures and processes.

Clinical Study Protocol – SWELL Study

6.1 Schedule of Events

Activity / Assessment	Screening	Treatment			Follow-up (in-office)		Extended Follow-up (remote)			
		Preprocedure	Procedure	Immediate Postprocedure	1 Week	3 Months (13 weeks)	6 Months (26 weeks)	12 Months (52 weeks)	24 Months (104 weeks)	36 months (156 weeks)
Window (days)	(-30)	(0)		(± 3)	(± 14)	(± 30)	(± 30)	(± 30)	(± 30)	(± 30)
Eligibility	X									
Consent	X									
Demographics / Medical History	X									
Physician Evaluations										
Nasal Assessment (visual, endoscopic)	X	X ¹		X	X	X				
CT imaging of SSB	X ²					X				
Current medication use (study relevant)	X			X ³	X	X	X	X	X	X
Participant Evaluations										
NOSE Scale	X ⁴					X ⁵	X	X	X	X
VAS nasal pain				X	X					
NRS ease of breathing	X					X	X	X	X	X
Participant Satisfaction Survey						X	X	X	X	X
SNOT-22	X					X	X	X	X	X
Study Procedure (includes anesthesia)			X							
Adverse Events	X			X	X	X	X	X	X	X

¹ Nasal Assessment do not need to be repeated if Screening and Treatment visits occur on the same day.

[figure not shown]
² CT should only be performed if your site was selected for the CT substudy and only after all other screening procedures and participant eligibility is confirmed.

³ Add any postprocedure medications to the medication log.

⁴ Baseline NOSE Scale Score for analysis is defined as the Screening score.

⁵ Primary analysis endpoint evaluation.

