Vivaer Treatment:	The Vivaer procedure will be performed in the study clinic using the Vivaer ARC Stylus and Aerin Console. The Vivaer ARC Stylus is a disposable handheld device capable of delivering bipolar radiofrequency energy to tissue when connected to the Aerin Console radiofrequency generating device. Participants will undergo bilateral treatment of the nasal airway in a single study procedure session. Each side of the nose will be treated as follows:

Clinical Study Protocol – SWELL Study

- Two (2) to six (6) nonoverlapping applications of RF energy are performed at the SSB per nostril.

The default treatment settings will be used for the study: temperature 60° C, power 4 watts, treatment time 18 seconds, and cooling time 12 seconds. No repeat (“touch up”) procedures will be permitted after the initial procedure through the end of the study (36 months).

Primary Endpoint:	The primary endpoint is improvement in self-reported Nasal Obstruction Symptom Evaluation (NOSE) Scale score from baseline recorded at the screening evaluation to 13 weeks after the procedure.
Secondary Endpoints:	
• Responder percent: A responder is defined as at least 1 NOSE Scale class improvement or an improvement (decrease) in NOSE Scale score of 20% or more from baseline to 13 weeks after the procedure.• Frequency of device-related and procedure-related serious adverse events, including frequency of septal perforation during the procedure, through the 3-month evaluation.
Study Hypotheses	Primary hypothesis: mean improvement in NOSE Scale score from screening to 13 weeks will exceed 25 points. Other hypothesis: the treatment effects will be maintained through the extended follow-up period of 36 months.

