5.2 Study Population

The target population for this study is adults suffering from symptoms attributed to NAO with evidence of SSB obstruction of the airway which may or may not include hypertrophied turbinates. This study requires severe or extreme symptoms demonstrated by a NOSE Scale score ≥ 55 and determination by the investigator that the SSBs are the primary or significant contributor to the nasal obstruction.

Participants who have had previous surgical treatment of the nasal valve in the past 6 months are not eligible to enroll in this study; however, it is anticipated that many participants will have already undergone rhinoplasty, septoplasty, IT reduction or other surgical procedures prior to being approached for participation in this study. Therefore, a history of those types of procedures does not exclude a participant from enrolling in this study. However, to ensure that changes in NOSE Scale score over

Clinical Study Protocol – SWELL Study

the course of follow-up are the result of the Vivaer procedure, prior surgical procedures must have been performed at least 6 months before the participant is enrolled in this study and no additional procedures should take place on the day of the Vivaer procedure or in the next 3 months.

Participants must meet all inclusion and no exclusion criteria listed below for participation in the study.

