5.2.1 Inclusion Criteria

1. Age 22 to 85 years (inclusively).
2. Seeking treatment for nasal obstruction and willing to undergo an office-based procedure.
3. Baseline NOSE score ≥ 55 .
4. Presence of SSB hypertrophy limiting visualization of the middle turbinate (MT) by more than 50%.
5. Reduction in size of the SSB after application of topical decongestant on a cotton plug directly to the SSB region.
6. Improvement in the symptoms of nasal obstruction after SSB decongestion suggesting that the SSB may play a role in nasal obstruction.
7. Willing and able to withhold anticoagulant medications during the perioperative period (3-day window on either side).
8. Willing and able to provide informed consent.
9. Willing and able to comply with the participant-specific requirements outlined in the study protocol.

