5.5.2 Study Success

The study will be considered a success if the mean improvement in NOSE Scale score from baseline (screening) to 13 weeks exceeds 25 points.

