6.4 Treatment Visit and Procedure (Day 0)

The treatment is summarized below and is comprised of the preprocedure, procedure and postprocedure as indicated on the Schedule of Events ([Section 6.1](#)). The treatment visit should occur within 30 days of the Screening Visit (study entry), once all inclusion and exclusion criteria have been met. Consult the Aerin Console Instructions for Use (IFU) for full detail of the standard treatment procedure and step-by-step instructions for preparation and use of the Vivaer ARC Stylus and Aerin Console.

Clinical Study Protocol – SWELL Study

Preparation (preprocedure)

The treatment will be performed in the study clinic within 30 days of study entry. The participant will be seated and positioned in the exam chair according to personal comfort and study physician's preference (eg, upright, reclined or supine). A nasal assessment (visual and endoscopic exam) will be performed on each side of the nose and for each nostril, including endoscopic video. This is to assess the configuration of the structural components of the lateral nasal wall (including the upper and lower lateral cartilage, their junction and the overlying mucosa), location of SSB and the MT to allow the study physician to map out and plan the areas of treatment. If the Screening and Treatment visits occur on the same day, the nasal assessment does not need to be repeated for Preprocedure.

Following the nasal assessment, it is recommended the study physician prepare the treatment area with a topical anesthetic agent (eg, lidocaine, tetracaine, etc.) and applying via spray, gel, or saturated pledget placed within the nose. After an appropriate amount of time, the SSB is then visualized with an endoscope and infiltrated in a submucosal plane with a small amount of local anesthetic to provide adequate tissue analgesia as well as tumescence to facilitate radiofrequency energy transfer. For example, cottonoid pledges saturated with 4% lidocaine are placed in the nasal passages adjacent to the septum; after 5 minutes, these pledges are removed and the swell body is injected bilaterally with 0.4 cc of 1% lidocaine with 1:100,000 epinephrine on each side.

Treatment administration

Once the nasal cavities have been anesthetized, participants will undergo bilateral treatment of the SSB in a single study procedure session. Each side of the nose will be treated as follows

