7.0 Statistical Considerations

7.1 Study Design

This is a prospective, multicenter, open-label, single-arm study to assess the Vivaer procedure for treatment of SSB to improve symptoms in those diagnosed with NAO. This study is designed to assess improvement in symptoms from prior to the procedure to a primary endpoint at 3 months after the procedure and out to 36 months.

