7.10 Primary Endpoint Analysis

The primary endpoint hypothesis of change from baseline to the 13-week endpoint will be analyzed using a paired t-test at the 1-sided alpha .025 level and presented as the mean change with associated 1-sided lower confidence bound.

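### The screening NOSE score that admits a participant (≥55) is also the analysis baseline, so regression to the mean counts, probably modestly, toward the 25-point goal

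*Combined protocol and SAP*

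**What the plan says.** Inclusion criterion 3 (section 5.2.1) is "Baseline NOSE score ≥ 55", and section 5.2 explains the intent: "This study requires severe or extreme symptoms demonstrated by a NOSE Scale score" of at least 55. The Schedule of Events (section 6.1) marks one pre-treatment NOSE, at screening, and none at the preprocedure visit. Table 1 in section 9.3.2 agrees: form 03 is listed at screening and not at the study procedure. Footnote 4 to the schedule then states: "Baseline NOSE Scale Score for analysis is defined as the Screening score".

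Everything confirmatory is measured from that score. The Protocol Summary defines the primary endpoint as "improvement in self-reported Nasal Obstruction Symptom Evaluation (NOSE) Scale score from baseline recorded at the screening evaluation to 13 weeks after the procedure". Section 5.5.2 says: "The study will be considered a success if the mean improvement in NOSE Scale score from baseline (screening) to 13 weeks exceeds 25 points". Section 5.5.1 defines a responder from the same baseline. The trial is a "prospective, multicenter, open-label, single-arm study" (section 7.1), and under section 7.10 the primary change "will be analyzed using a paired t-test at the 1-sided alpha .025 level".

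Treatment may follow screening by up to 30 days (section 6.4) or fall on the same day (footnote 1 of the schedule). The documents mention neither regression to the mean nor a repeat baseline, and they do not derive the 25-point goal in a way that allows for it. The only stated sensitivity analysis concerns missing data (section 7.6).

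**The concern.** A NOSE score is part stable severity and part day-to-day error. Admitting only people who score 55 or more favors those whose error was upward that day, so the enrolled group's screening mean sits above its own long-run mean. When the group is measured again, the average falls back even if nothing was done. A concurrent control would show the same fall and cancel it; here there is none.

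The bias runs in one direction, toward passing. At stake are how much of the reported improvement can be attributed to the procedure, and the chance of passing if the attributable improvement is close to 25 points. Section 5.2 restricts other nasal procedures so that NOSE changes can be credited to the treatment. Regression to the mean is another non-treatment change, and the plan does not address it.

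**Working it through.** **1. The plan's own figure.** Section 7.3 gives an expected change of -50, SD 20, n = 70, one-sided alpha 0.025 and power 0.99. The noncentrality is (50 - 25)/20 × √70 = 10.46 on 69 df, so power exceeds 0.9999; the stated 0.99 is met. The observed mean improvement needed to reject is 25 + 1.995 × 20/√70 = 29.8 points.

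**2. Size of the regression.** For selection at a cut-off c from a population with mean μ, SD σ and test-retest reliability ρ, the expected fall without treatment is

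(1 - ρ) × σ × φ(z) / (1 - Φ(z)), with z = (c - μ)/σ.

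NOSE moves in 5-point steps, so c = 52.5. The values of μ, σ and ρ are assumptions: μ 50-70, σ 20, ρ 0.7-0.9.

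- μ = 50: z = 0.125, and 20 × 0.396/0.450 = 17.6. Times 0.3 (ρ = 0.7), this is 5.3 points.
- μ = 60: z = -0.375, and 20 × 0.372/0.646 = 11.5. Times 0.1, 0.2 and 0.3, this is 1.2, 2.3 and 3.5 points.

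Simulation on the bounded 0-100 scale in 5-point steps agrees: 5.4 points for μ = 50 at ρ = 0.7; 1.2, 2.4 and 3.5 for μ = 60; and 0.7 for μ = 70 at ρ = 0.9. The range is 0.7-5.4 points, or 3% to 22% of the 25-point goal.

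**3. An anchor from the documents.** Section 1.0 reports, for the earlier Vivaer study of the nasal valve, a 6-month mean of 24.7 after an average decrease of 54.5 (68.6%). The implied baseline is 24.7 + 54.5 = 79.2, or 54.5/0.686 = 79.4. Unselected means of 50, 60 and 70 give enrolled baselines of only 67.6, 71.3 and 76. Reaching about 79 needs an unselected mean near 75. Then z = -1.125, and 20 × 0.212/0.870 = 4.87. Times 0.1, 0.2 and 0.3, this is 0.5, 1.0 and 1.5 points.

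**4. Effect on the success decision.** Suppose the change attributable to treatment is exactly 25 and the regression adds R points. The test statistic then has noncentrality R/20 × √70.

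| R (points) | Case | Chance of success |
|---|---|---|
| 0 | no bias | 0.025 |
| 0.5 | baseline near 79, ρ = 0.9 | 0.04 |
| 1.0 | baseline near 79, ρ = 0.8 | 0.06 |
| 1.5 | baseline near 79, ρ = 0.7 | 0.09 |
| 2.4 | μ = 60, ρ = 0.8 | 0.17 |
| 5.4 | μ = 50, ρ = 0.7 | 0.61 |

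Away from 25 the effect fades. At an attributable change of 20, R = 2.4 gives 0.001 and R = 5.4 gives 0.036. At 35, power without any bias is already 0.985.

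**5. Responder rate.** With no treatment effect, σ = 20 and μ = 50-70, the simulated responder rate from the screening baseline is 16% (μ = 70, ρ = 0.9) to 41% (μ = 50, ρ = 0.7). From a separate second baseline it is 14% to 28%. Reuse of the screening score therefore accounts for 16 - 14 = 2 to 41 - 28 = 13 percentage points.

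**6. Power with a fresh baseline.** If a separate baseline took 10 points off the expected 50, power at n = 70 would still exceed 0.9999.

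**The case against.** The strongest reply is that the test is valid for what it claims. The endpoint and hypothesis are expressly change from screening, and the paired t-test controls error for that quantity. A reader might infer that the 0.025 level is broken; the documents do not support that. What is unprotected is the reading of that change as a treatment effect, which is a limit of any openly declared single-arm design. This stands, and the point is about attribution.

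Second, the size is assumed. The only baseline evidence in the documents points to 0.5-1.5 points, and 5.4 points with 0.61 comes from the corner furthest from it. This also stands, with the caveat that the earlier study treated the nasal valve and not the swell bodies, so it is a guide only.

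Third, a reader might take the 16-41% no-effect responder rate as the product of the reused baseline. Most of it is measurement noise combined with a lenient rule: a class change can be a single 5-point step, such as 80 to 75 or 55 to 50. A new baseline would not remove that part. Nor is the secondary claim in danger: at a true rate of 41%, the chance of reaching the exact-test cut-off of 48/70 is about 3 in a million.

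Fourth, same-day screening and treatment is allowed, so a repeat score corrects only some participants. The documents do not say how many. This limits the remedy, but the bias in the remaining participants is still worth removing.

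**Conclusion.** The structural point holds: the qualifying score is the baseline, it is the only pre-treatment NOSE, and nothing in the design or analysis offsets regression to the mean. Its likely size is modest. The figures rest on an assumed SD of 20 and reliability of 0.7-0.9, neither of which the documents supply, and on either the enrolled baseline near 79 or the unselected mean of 50-70. The result matters for the decision only if the attributable change lies close to 25.

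One might infer that the trial could pass on regression alone. The calculations do not support this: even with wider assumptions (mean 50-70, SD 15-25, reliability 0.5-0.9) the bias is about 0.3-12 points, well short of 25. At the planned change of 50, pass or fail is unaffected. What remains at any true effect is some overstatement of the mean change and the responder rate. This is a worthwhile, inexpensive improvement and not a defect that invalidates the primary test.

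**What to change.** Collect NOSE (form 03) at the preprocedure visit, before anesthetic, whenever screening and treatment fall on different days. Use the screening score for eligibility only, and the preprocedure score as the analysis baseline for those participants. Keep the screening score for same-day participants, and report the primary result with and without them.

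Align the text accordingly: footnote 4 and the schedule (also reproduced in the Protocol Summary), the primary endpoint definition, sections 5.5.1, 5.5.2, 7.2 and 7.3, and Table 1. Sections 5.4.3 and 7.12 already refer to a preprocedure NOSE score that the schedule does not separately collect; the change would give that wording a real measurement.

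The cost is one five-item questionnaire at an existing visit, with no meaningful loss of power and no change to eligibility. The drawbacks are a slightly smaller reported improvement, no correction for same-day participants, and two baseline sources within one analysis. If the schedule cannot change, a prespecified sensitivity analysis that subtracts regression to the mean over a stated range of reliability, with a justification of the 25-point goal, would be a weaker substitute.

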6.2 Participant Flowchart

6.3 Enrollment and Screening Assessment

Screening

During screening, the investigator or designated research staff will perform an evaluation of the study candidate for study eligibility, which will include a history and physical examination of the nasal area bilaterally, review of overall medical history, history of allergies, understanding of general health and discussion of any conservative measures used for NAO.

Participants must be diagnosed with NAO prior to entry into the study. While the availability of the study may be discussed with a prospective participant without first obtaining consent, informed consent must be obtained prior to initiation of any clinical procedures dictated by the protocol that are performed solely for the purpose

Clinical Study Protocol – SWELL Study

of determining eligibility to participate in the study. A participant will be considered as being entered into the study once informed consent is provided. Once the participant is entered into the study, screening assessments are completed, and the study treatment (preprocedure, procedure and immediate post procedure) should be completed **within 30 days**.

Informed Consent

Informed consent must be obtained in accordance with FDA regulation 21 CFR Part 50 and ISO 14155. The investigator or designated staff member is responsible for ensuring that IRB current and approved informed consent is obtained for each participant prior to participation in the study, or before undergoing any procedure specific to the clinical investigation. The participant must be fully counseled with an explanation of the study background, non-randomized nature of the study, study procedure, follow-up schedule, and informed of their options, risks and benefits, and have every opportunity to ask questions about participation in the study. Any new information obtained during the course of the study that may affect the health of the participant or their decision to continue in the study will be provided to the participant. This process includes a thorough explanation of the informed consent document that the participant will be asked to sign and date acknowledging that they understand and desire to participate in the study. The explanation and discussion should be conducted in such a way as to:

- answer the participant's questions,
- avoid coercion or influence of participant to participate in the study,
- ensure the participant understands that their legal rights are not waived at any time,
- use language at a level the participant can understand, and
- ensure the participant understands that after providing signature on the informed consent, the participant may still withdraw at any time before, during or after study treatment.

A copy of the signed informed consent document should be provided to the participant.

Evaluation of Inclusion and Exclusion Criteria

The Screening Visit / Study Eligibility eCRF will be used to document the participant's eligibility status.

Screening Data and Assessments

The following data will be obtained at Screening and recorded on the Screening Visit – Demographics, Treatment History and Nasal Exam eCRF:

- Demographics
 - Sex
 - Height (inches)

Clinical Study Protocol – SWELL Study

- Weight (pounds)
- BMI
- Date of birth
- Race / Ethnicity
- Medical history, Nasal Symptoms, History of Treatments, General Nasal Exam
 - History (duration) of nasal obstruction
 - History of nasal trauma
 - Related nasal symptoms
 - History of rhinitis (allergic, nonallergic), sinus disease, and/or obstructive sleep apnea
 - participant-reported, Medication/treatments used to address nasal obstruction and/or related symptoms, including continuous positive airway pressure (CPAP)
 - Evaluation of significant anatomic conditions that could affect treatment outcome (eg, severe septal deviation, turbinate enlargement, nasal polyps, ptotic nasal tip, and/or other external nasal deformity)
- Nasal assessment (visual and endoscopic exam) for each nostril including representative video of each nasal.
- (Selected sites only)CT to assess changes in the SSB after treatment will be collected at a subset of study sites.
- Current use of medication for symptoms of nasal obstruction will be detailed on the Nasal Medication Log
- Current use of devices, or other therapies.
- Screening NOSE Scale score (completed by participant).
- NRS ease of breathing score (completed by participant).
- SNOT-22 (completed by participant).
- Adverse Events.

6.4 Treatment Visit and Procedure (Day 0)

The treatment is summarized below and is comprised of the preprocedure, procedure and postprocedure as indicated on the Schedule of Events ([Section 6.1](#)). The treatment visit should occur within 30 days of the Screening Visit (study entry), once all inclusion and exclusion criteria have been met. Consult the Aerin Console Instructions for Use (IFU) for full detail of the standard treatment procedure and step-by-step instructions for preparation and use of the Vivaer ARC Stylus and Aerin Console.

Clinical Study Protocol – SWELL Study

Preparation (preprocedure)

The treatment will be performed in the study clinic within 30 days of study entry. The participant will be seated and positioned in the exam chair according to personal comfort and study physician's preference (eg, upright, reclined or supine). A nasal assessment (visual and endoscopic exam) will be performed on each side of the nose and for each nostril, including endoscopic video. This is to assess the configuration of the structural components of the lateral nasal wall (including the upper and lower lateral cartilage, their junction and the overlying mucosa), location of SSB and the MT to allow the study physician to map out and plan the areas of treatment. If the Screening and Treatment visits occur on the same day, the nasal assessment does not need to be repeated for Preprocedure.

Following the nasal assessment, it is recommended the study physician prepare the treatment area with a topical anesthetic agent (eg, lidocaine, tetracaine, etc.) and applying via spray, gel, or saturated pledget placed within the nose. After an appropriate amount of time, the SSB is then visualized with an endoscope and infiltrated in a submucosal plane with a small amount of local anesthetic to provide adequate tissue analgesia as well as tumescence to facilitate radiofrequency energy transfer. For example, cottonoid pledges saturated with 4% lidocaine are placed in the nasal passages adjacent to the septum; after 5 minutes, these pledges are removed and the swell body is injected bilaterally with 0.4 cc of 1% lidocaine with 1:100,000 epinephrine on each side.

Treatment administration

Once the nasal cavities have been anesthetized, participants will undergo bilateral treatment of the SSB in a single study procedure session. Each side of the nose will be treated as follows

- A nasal speculum is inserted into the nostril and opened to visualize the treatment area. The Vivaer ARC Stylus will then be inserted to access the treatment area. The Stylus will be connected to the Aerin Console generator and the RF energy level will be set on the generator.
- Two (2) to six (6) nonoverlapping applications of RF energy are performed at the SSB per nostril.
- For the SSB, Vivaer ARC stylus default settings will be employed. ([Figure 4](#)).

Figure 4. Vivaer ARC Stylus applied at SSB

The default settings for the Vivaer ARC Stylus:

Temperature	60° C
Power	4 Watts
Treatment Time	18 secs
Cooling Time	12 secs

The Aerin Console is activated by depressing the foot pedal. With the Vivaer ARC Stylus pressed against the tissues in the desired treatment locations, the foot pedal is depressed, and the Stylus is gently pressed against the nasal tissues to deliver RF energy to the tissues consistent with the IFU. A tone sounds when the Console is activated, signifying that energy is being delivered through the Stylus. The tone stops when the pedal is released, and RF energy is no longer being delivered.

No repeat ("touch-up") procedures will be permitted during the study follow-up period. Additionally, for the purposes of this study, no other concomitant treatments are permitted during this treatment or the follow-up period.

Procedure data collection

Data relating to the procedure and the products used will be recorded on the Study Procedure eCRF. The following information will be recorded:

- Date of procedure.
- Procedure and postprocedure medications (including anesthesia).
- Aerin Console serial number.
- Procedure start and end times.
- Aerin Console settings.
- Treatment duration and number of sites treated for SSB.
- Occurrence of device malfunctions, protocol deviations, and/or adverse events.

